4. STATISTICAL CONSIDERATIONS

4.1 Sample Size and Power

The primary analysis will be based on HIV incidence during Steps 1 and 2. As described previously, we assume that participants will be followed between 81 (latest enrollees) and 185 (earliest enrollees) weeks in Steps 1 and 2 (1.6 – 3.6 years), with a uniform distribution of enrollments over a two-year period. Thus, average time in Steps 1 and 2 will be 133 weeks (2.6 years). Sample size calculations are based on the following assumptions:

- Background HIV incidence, in the absence of any PrEP, is 3.5% per year
- Both CAB LA and TDF/FTC are 85% effective when used with 100% adherence
- 2.5% one-sided type I error rate and 90% power at the indicated alternative
- Average follow-up duration of 2.6 years (range: 1.6 – 3.6 years)
- Maximum 5% lost-to-follow-up per year

Table 4.1 presents five scenarios and associated total sample sizes. All are superiority designs. The first scenario assumes that adherence to TDF/FTC and CAB/CAB LA will be 50% and 85%, respectively, averaged over the entire Step 1 and 2 follow-up period. The second and third scenarios assume a higher adherence to TDF/FTC (second line) and lower adherence to CAB LA (80%) (third line) (these scenarios are considered unlikely). The last two scenarios retain the conservative assumption of 80% adherence to CAB LA and assume lower adherence to TDF/FTC of 45% and 48%. The largest blinded trials of TDF/FTC among women in a similar setting have shown even lower adherence than assumed in Table 4.1.

Given this history we believe that a sample size of at least 3,128 (111 events for a fixed sample size trial; we will target 114 events to allow for interim monitoring) provides an adequate degree of robustness against uncertainties in adherence rates to the two drug regimens. The trial will continue until we reach 114 events, or a stopping boundary is crossed (see below).

Table 4.1. Five Case Scenarios

Adherence		HIV Incidence (%/year) ¹				
TDF/FTC	CAB LA	TDF/FTC	CAB LA	RR	Number Events	Sample Size
.50	.85	2.01	0.97	.48	78	2352
.55	.85	1.86	0.97	.52	98	3112
.50	.80	2.01	1.12	.56	125	3590
.48	.80	2.07	1.12	.54	111	3128
.45	.80	2.16	1.12	.52	98	2686

¹Background incidence is reduced by a weighted average of fully adherent and non-adherent individuals e.g. 2.01 = $3.5 * ((1 - .85) * .5 + 1 * (1 - .5))$

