4.1.1 Sample Size Calculation and Monitoring for Efficacy and Harm

Table 1 reviews the key sample size assumptions. We propose five analyses of the 084 data (four interim and one final). Figure 1 shows the times of the interim analyses and the expected accumulation of participants and information (HIV events) over the course of the trial (assuming a constant incidence). The times of the interim analyses are chosen to correspond to the times of the DSMB reviews (every six months). No interim analyses are proposed prior to 1.5 years because of the small amount of information (HIV events) expected early in the trial. The software nTerim 3.0 was used for calculations.

Table 1. Key sample size calculation parameters and results. EOS = end of steps 1 and 2.

Parameter	Value	Comment
Test Significance level, α (2 sided)	0.05	
Average duration of follow-up	133 wks	$(81 + 185)/2$
Proportion uninfected at EOS, Cab	.9718	$\text{Exp}(-.0112 * 133/52)$ (1.12%/yr incidence)
Proportion uninfected at EOS, TDF/FTC	.9484	$\text{Exp}(-.0207 * 133/52)$ (2.07%/yr incidence)
Hazard ratio	.54	Assuming constant hazard in each arm
Power	90%	

Number of events	114	Slightly inflated from fixed sample size 111 due to interim monitoring
Total sample size	3257	2834/.87 where overall retention = .87
Interim monitoring times (expressed as % information)	.22, .39, .59, .78, 1	Corresponds to 6-month intervals, starting at 1.5 years

Figure 1. Planned accumulation of sample size and statistical information, along with proposed times of interim analyses, based on HPTN 084 study design.

[figure not shown]

Table 2 provides detailed information on monitoring the trial for early stopping at the interim analyses. The O'Brien-Fleming spending function is used to determine stopping boundaries. By the time of the first or second analysis we should have a better understanding of enrollment rates and HIV incidence; the timing of the final 3-4 analyses may be modified at that time. Any modifications, if needed, will use the O'Brien-Fleming spending function applied to the cumulative information available at the time of the analysis.

Table 2. Interim analysis plan for monitoring HPTN 084 based on expected accrual and HIV incidence rates. Ho: RR = 1; Ha RR = .54. Type I error rates (a) in the table are for 2-sided tests.

Time (years)	% Information	Expected no. events	Efficacy boundary (Z)	Harm boundary (Z)	Efficacy boundary (RR) [#]	Nominal α	Cumulative α	Cumulative Stop Prob. under Ha

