1.5*	22	25.3	-4.64	4.64	.04	.000001	.000001	0.1
2.0	39	44.8	-3.40	3.40	.30	.00066	.00066	8.7
2.5	59	67.0	-2.70	2.70	.50	.00682	.00704	42.7
3.0	78	89.2	-2.32	2.32	.60	.02010	.0223	72.2
3.56	100	114	-2.02	2.02	.68	.0429	.05	90.0

* Removing the first interim analysis has virtually no effect on the boundaries at subsequent times

RR boundary = (#events Cab/# events TDF), conditional on expected number of events; these RR correspond to approximately 1, 10, 22, 33, 46 events in the CAB arm, respectively

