
Ho: HR = 1

Ha: HR < 1

A two-sided test with $\alpha = .05$ will be used. The estimated hazard ratio (HR), a 95% confidence interval, and a p-value for the hypothesis shown above will be given. If the number of events is small (<40) then the p-value will be confirmed using a permutation test based on 100,000 random permutations of the treatment assignments; if there is a meaningful difference between the permutation and asymptotic procedures, the permutation p-value will be used. Treatment efficacy will be estimated as $TE = 1 - HR$.

If the trial is stopped early (prior to the final analysis), then the primary results will be reported as a bias-adjusted mean HR and design-adjusted 95% CI (Emerson S and Fleming TR. Symmetric Group Sequential Test Designs. *Biometrics* 45:904-923, 1989).

7.3.1.1. Sensitivity of the Primary mITT results:

The following sensitivity analyses are proposed to aid in interpretation of the primary ITT results :

- A per-protocol analysis, excluding participants with exclusionary protocol violations, will be conducted if the number of participants affected exceeds 2% of the enrolled population.
Population: Per Protocol
This analysis will be identical to the mITT analysis, except that for partial exclusions, the follow-up will be censored on the last non-missing HIV test result date on or prior to the date of the deviation that resulted in exclusion from the per-protocol population.
- A supportive analysis will be presented using the OBSP censoring in the Injection (Step 2) Efficacy population (see OBSP censoring definitions in appendix B), where study follow-up is censored when a participant does not receive blinded injection study product on time.
- In this active control trial, the superiority of CAB LA is predicated in part on incomplete adherence to daily oral TDF/FTC. Specifically, we assume that overall adherence to TDF/FTC will be less than 50%. If adherence to TDF/FTC is high (greater than 50%) then, as described in section 7.8.4 of the protocol, a supportive non-inferiority (NI) analysis of CAB LA versus TDF/FTC may provide valuable information for interpreting the trial results.

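### The primary test in section 7.3.1 is set at two-sided .05 with an ordinary 95% CI, while Table 2 leaves the final look a nominal .0429

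*SAP*

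**What the plan says.** Section 4.1 sizes the trial for "2.5% one-sided type I error rate and 90% power at the indicated alternative". Section 4.1.1 then states "We propose five analyses of the 084 data (four interim and one final"), with stopping boundaries from an O'Brien-Fleming spending function. Table 1 lists .05 against "Test Significance level, α (2 sided"). If the looks are retimed, the boundaries are to come from the "spending function applied to the cumulative information available at the time of the analysis". The last row of Table 2 reads "3.56 100 114 -2.02 2.02 .68 .0429 .05 90.0": at 114 events the boundary is |Z| = 2.02, the critical relative risk .68, the nominal two-sided level .0429, the cumulative level .05 and the cumulative stopping probability under the alternative 90.0%.

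Section 7.3.1 specifies a Wald test from a site-stratified Cox model. On the level it says "A two-sided test with $\alpha = .05$ will be used". On reporting it says "The estimated hazard ratio (HR), a 95% confidence interval, and a p-value for the hypothesis shown above will be given". The only adjustment for sequential monitoring is conditional: "If the trial is stopped early (prior to the final analysis), then the primary results will be reported as a bias-adjusted mean HR", with a design-adjusted 95% interval. Section 7.3.1 does not cite Table 2, the spending function or the separate Interim Monitoring Guidelines mentioned in section 1.

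**The concern.** Two parts of the SAP govern the same test at 114 events and do not give the same criterion. Table 2 requires |Z| of about 2.025. Section 7.3.1, the text an analyst programs from, gives a .05 test and a 95% interval, which correspond to |Z| = 1.96 unless something says otherwise. Because adjustment is limited to early stopping, an analyst with a full-term trial has no instruction to adjust anything.

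Two things are at stake. If the final look is tested literally at .05, the alpha already spent at the interim looks is spent again and the overall error exceeds the 5% two-sided (2.5% one-sided) level of the design. If the decision is instead taken from Table 2, the published p-value and interval can still contradict it, and the SAP has no rule for which prevails in the primary superiority claim.

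**Working it through.** **Inputs.** Information fractions .22, .39, .59, .78, 1 (Table 1); O'Brien-Fleming spending, two-sided .05 (4.1.1); 114 events, alternative .54 (Tables 1 and 2); 1:1 allocation (4.2). The standard error of the log hazard ratio is taken as 2/√114 = .1873.

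**1. Reproduce Table 2.** With cumulative two-sided spending α(t) = 4[1 − Φ(z.9875/√t)], that is .025 on each side, recursive numerical integration gives:

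| Information | Boundary, computed | Boundary, printed | Nominal α, computed | Nominal α, printed | Cumulative α, computed | Cumulative α, printed |
|---|---|---|---|---|---|---|
| .22 | 4.637 | 4.64 | .000004 | .000001 | .000004 | .000001 |
| .39 | 3.405 | 3.40 | .00066 | .00066 | .00066 | .00066 |
| .59 | 2.705 | 2.70 | .00682 | .00682 | .00704 | .00704 |
| .78 | 2.325 | 2.32 | .0201 | .02010 | .0223 | .0223 |
| 1 | 2.0247 | 2.02 | .0429 | .0429 | .05 | .05 |

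Table 2 is reproduced except for the first-look alpha, which is too small to matter here. The printed 2.02 is a rounding: Z = 2.02 exactly has two-sided p = .0434, whereas .0429 corresponds to 2.0247.

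**2. Overall error under each final criterion**, keeping the four interim boundaries:

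| Final criterion | Two-sided error | One-sided error | Power at HR .54 |
|---|---|---|---|
| \|Z\| > 1.96 (7.3.1 read literally) | .0562 | .0281 | .912 |
| \|Z\| > 2.0247 (Table 2) | .0500 | .0250 | .902 |

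Using the printed, rounded interim boundaries with a final 1.96 gives .0563. Dropping the first look also gives .0563.

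**3. Where the two criteria disagree.** Critical HR = exp(−Z × 2/√114):
- Z = 1.96: exp(−1.96 × .1873) = .693
- Z = 2.0247: exp(−2.0247 × .1873) = .684 (Table 2 prints .68)

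The disputed band is therefore a hazard ratio of about .684 to .693.

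**4. How often the trial ends there.** The probability of reaching the final look is .978 under the null and .274 at HR .54. The probability of reaching it and landing in the band on the efficacy side is .0031 under the null, .0097 at HR .54 and .0225 at HR .69.

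**5. A worked case, final Z = −2.00.** HR = exp(−2.00 × .1873) = .688.
- Unadjusted: p = .0455; 95% CI exp(−.3746 ± 1.96 × .1873) = .476 to .993, excluding 1.
- Table 2: 2.00 < 2.0247, so the boundary is not crossed.
- Stage-wise ordering: p = .052; 95% CI .478 to 1.004, in agreement with Table 2.

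At Z = −2.0247 exactly, stage-wise ordering gives p = .0500 and an upper limit of 1.000, so its p-value and interval change verdict where the boundary does.

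**The case against.** The strongest reply is that .05 in section 7.3.1 is simply the trial-wide level. Table 1 gives .05, the cumulative column of Table 2 ends at .05, the final analysis is one of the five planned looks, and section 7.2.2 sends the reader to 4.1.1. On that reading the two sections are compatible, Table 2 governs the decision, and the 5.6% arises only if an analyst ignores the table's last row. The Interim Monitoring Guidelines, which are not available here, may also settle it.

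Much of this is reasonable, and the overall-level reading may well be what was intended. But section 7.3.1 does not say so, and section 7.2.2 links efficacy monitoring to 4.1.1 without linking the final test to Table 2. More importantly, that reading does not repair the reporting. Adjustment is still confined to early stopping, so the full-term p-value and interval are unadjusted and can contradict the boundary, as in the worked case.

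Two further points stand. The effect is small and arises only at the final look. Also, full design adjustment is not the only remedy: reporting the nominal level beside the interval would remove most of the ambiguity.

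**Conclusion.** The point holds and should be fixed. As written, section 7.3.1 does not match the SAP's own final boundary. Read literally, it raises overall type I error from 5.0% to about 5.6% two-sided (2.5% to 2.8% one-sided). Read as the overall level, it still allows a full-term p-value and interval that contradict Table 2 for a hazard ratio of about .684 to .693. The chance of ending in that band is 0.3% under the null, 1.0% at HR .54 and 2.3% at HR .69, so the practical risk is low, but it falls on the primary superiority decision.

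These figures assume the Table 2 information schedule, 114 final events and a standard error of 2/√114. A different look schedule would change the exact final nominal level. The Interim Monitoring Guidelines could contain a rule that resolves this, but section 7.3.1 does not point to them.

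**What to change.** Add to section 7.3.1:
- .05 is the overall two-sided type I error across the planned analyses.
- The final test uses the O'Brien-Fleming spending boundary at the information actually accrued. On the Table 2 schedule this is nominal two-sided p ≤ .0429, |Z| about 2.025.
- The interval and p-value are design-adjusted to agree with that boundary whether or not the trial stops early, and the ordering used is named. Stage-wise ordering agrees with the boundary; if another is chosen, its agreement should be confirmed.

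If the team prefers to keep an unadjusted interval, the minimum is to state that success is judged against the Table 2 boundary and to report the interval at the matching level (1 − .0429, about 95.7%).

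The cost is a few sentences and no new data. Relative to Table 2 no criterion changes. Relative to a literal reading of 7.3.1, the critical hazard ratio moves from .693 to .684 and power at HR .54 from 91.2% to 90.2%, still at the planned 90%.

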7.3. Endpoint Analyses

7.3.1. Primary Efficacy Analysis

Objective: To evaluate the relative efficacy of oral CAB/CAB LA (oral run-in and injections, Steps 1 and 2) vs. daily oral TDF/FTC for HIV prevention

Population: mITT population

Outcome: Time of HIV-1 Infection (censored at end of step 2)

Time from randomization to HIV-1 infection (see definition in appendix B) will be the primary endpoint for this analysis. HIV-1 status will be assumed to be negative for any missing visits prior to the first positive HIV-1 test (unless defined differently by the endpoints committee prior to analysis). Person-time and HIV events will be included in this analysis based on each individual's scheduled participation in steps 1 and 2, as determined at randomization. Specifically, individuals who refuse/discontinue injections, pills or both, or who receive open-label study product (e.g. due to pregnancy) will be included in this analysis in their original randomization arm for the duration of their originally scheduled participation in Steps 1 and 2. Individuals who drop out of the study and refuse further testing prior to completion of follow-up and individuals who die prior to completion of follow-up will be treated as uninformatively censored as of their last valid HIV test.

Descriptive analysis: The number of participants, number of infections and cumulative person-years will be presented by arm and overall. The HIV incidence rate will be calculated as the total number of participants with confirmed incident HIV infection during steps 1 and 2 of study follow-up, divided by the person-years accumulated in each arm. Corresponding 95% CIs will be calculated based on Poisson assumptions. Cumulative incidence over follow-up for each arm will be computed using product limit estimates and plotted with 95% CIs.

Statistical Analysis: The primary “intent-to-treat” analysis will be based on a Cox model using time to HIV detection (as defined above) as the outcome. The model will include an indicator for intervention arm (TDF/FTC = 0; CAB LA = 1) and be stratified by site. Consistent with an intent-to-treat analysis, women will be included in the analysis in their original randomization group whenever endpoint information is available within the prespecified timeframe of follow-up. Participants who remain HIV-1 uninfected will be censored at their last negative HIV test. A formal statistical comparison between study arms will be performed using a Wald test of the hypothesis

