Box plots of local laboratory values will be generated for baseline values and for values measured during the study by treatment arm and visit. Each box plot will show the first quartile, the median, and the third quartile. Outliers will also be plotted. If appropriate, horizontal lines representing boundaries for abnormal values will be plotted. The number (percentage) of participants with local laboratory values recorded as meeting Grade 3 AE criteria or above as specified in the DAIDS AE Grading Table will be tabulated by treatment arm. Reportable clinical laboratory abnormalities without an associated clinical diagnosis will also be included in the tabulation of AEs described above.

- **Efficacy Reports**

The efficacy reports will be shared with the DSMB committee when required as per the analysis methodology mentioned in section 7.2.2 and 7.3.1 of the SAP ()above.

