- If HIV uninfected At OBSP censoring time, study time will be calculated as the number of days between enrollment and the last visit with HIV status at or before the OBSP censoring time.

Primary endpoint:

- Only infections that are confirmed by the EAC and detected within the analysis timeframe at the time of the final primary analysis adjudication (date of first positive visit as determined by the EAC within the analysis timeframe) will be considered. Infections that are not confirmed by the EAC or that occur out of the analysis timeframe will not be included as primary endpoints.

Interim Analysis (mITT and OBSP) specification

Interim analysis procedures will follow the primary analysis definitions above with the exception that the analysis timeframe will be truncated at the interim-analysis data cut date, as follows.

mITT analysis

- All data from enrollment through the interim analysis cut date will be considered

OBSP analysis

- If there is an injection delay prior to the data cut, all data up to the last visit with HIV status determined that occurred prior to the data cut date and within 6/10 weeks for the first/subsequent injection of the last non-delayed injection will be considered.
- If there is no injection delay prior to the data cut point, data included as for the ITT analysis

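### First interim look only: Table 2 row 1 prints alpha .000001 where its own Z = 4.64 gives about .0000035, and the 100,000-permutation fallback cannot resolve a boundary that small

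*SAP*

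**What the plan says.** SAP section 4.1.1, Table 2, plans looks at 25.3, 44.8, 67.0, 89.2 and 114 expected events, with boundaries from the O'Brien-Fleming spending function. Row 1 (1.5 years, 22% information) gives Z = ±4.64, an RR boundary of .04, and .000001 for both nominal and cumulative alpha. The table heading says that the alphas "in the table are for 2-sided tests". A footnote adds that "these RR correspond to approximately 1, 10, 22, 33, 46 events in the CAB arm, respectively", and another that "Removing the first interim analysis has virtually no effect on the boundaries at subsequent times".

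Section 7.3.1 fixes the test: "A formal statistical comparison between study arms will be performed using a Wald test of the hypothesis", from a Cox model stratified by site. With fewer than 40 events the p-value is to be "confirmed using a permutation test based on 100,000 random permutations of the treatment assignments", and "if there is a meaningful difference between the permutation and asymptotic procedures, the permutation p-value will be used". The link to the interim looks is in section 9.1: "The efficacy reports will be shared with the DSMB committee when required as per the analysis methodology mentioned in section 7.2.2 and 7.3.1". Section 7.2.2 only refers back to 4.1.1. The Introduction says that a more detailed interim plan is kept in separate Interim Monitoring Guidelines, which are not at hand.

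**The concern.** Two things in row 1 do not fit together.

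(a) The Z and alpha columns should express one threshold, and .000001 is not the two-sided tail area of 4.64.

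(b) The methods named for the DSMB's efficacy report cannot judge that threshold. A Wald statistic has a ceiling when events are few, and a Monte Carlo p-value cannot be finer than its number of draws allows. Of the planned looks, only the first falls below 40 events, so it is the only planned look that would call on the fallback.

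At stake is whether an extreme early split would be recognised as a crossing, and whether two analysts following the SAP would reach the same answer.

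**Working it through.** **Inputs.** From SAP 4.1.1: overall two-sided alpha .05; information fractions .22, .39, .59, .78, 1; 25.3 events and Z = 4.64 at look 1; HR .54 under the alternative. From 7.3.1: B = 100,000 permutations below 40 events. Assumption for the small-count work: equal exposure in the arms and site strata ignored, so that under the null each event falls in either arm with probability one half.

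**Reproducing Table 2.** The two-sided O'Brien-Fleming spend is 4 × [1 − Φ(z(.0125)/√t)], where z(.0125) is the upper 1.25% normal point.
- t = .39, .59, .78 gives .00066, .00704, .0223, as printed.
- Group-sequential integration at the printed fractions gives Z = 4.637, 3.405, 2.705, 2.325, 2.025. The printed values are 4.64, 3.40, 2.70, 2.32, 2.02.
- t = .22 gives 3.53e-6, where the table prints .000001.

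Directly, 2 × [1 − Φ(4.64)] = 3.48e-6. Rounding of Z (4.635 to 4.645) moves this only between 3.40e-6 and 3.57e-6. A two-sided .000001 needs Z = 4.89. The one-sided value, 1.74e-6, would truncate to .000001, but the table is labelled two-sided.

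**Wald statistic at 25 events.** With k events in the CAB arm, |Z| = ln[(25 − k)/k] / √[1/k + 1/(25 − k)]:

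| k | Wald | Score, (25 − 2k)/√25 | Exact two-sided p |
|---|---|---|---|
| 0 | undefined | 5.00 | 6.0e-8 |
| 1 | 3.11 | 4.60 | 1.55e-6 |
| 2 | 3.31 | 4.20 | 1.94e-5 |
| 3 | 3.24 | 3.80 | 1.57e-4 |
| 4 | 3.04 | 3.40 | 9.1e-4 |

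The Wald value never approaches 4.64. Simulated site-stratified Cox fits, on an assumed layout of 20 sites of 125 women, reached at most 3.73.

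The row 1 RR boundary fits a score-type Z. Setting (25.3 − 2k)/√25.3 = 4.64 gives k = (25.3 − 23.34)/2 = 0.98, and RR = 0.98/24.32 = .040, as printed.

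**Permutation p-value, B = 100,000, against 3.48e-6.**
- Convention (count+1)/(B+1): the minimum is 1/100,001 = 1.0e-5, about 2.9 times the boundary, so not even 0 v 25 crosses. A crossing is possible only from B = 1/3.48e-6 − 1, about 287,000.
- Convention count/B: the limit is 100,000 × 3.48e-6 = 0.35 exceedances, so a crossing means none. With the exact p above, the chance of none is .856 for 1 v 24 and .143 for 2 v 23. Once such a split has occurred, each is misjudged in about 14% of seeds.

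The SAP states neither the convention nor which statistic is permuted. If it is the Wald Z, 1 v 24 ranks as less extreme than 2 v 23 and 3 v 22, so its p is at least 2 × (25 + 300 + 2,300)/2^25 = 1.6e-4.

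**Where the problem ends.** The spend passes 1e-5 at t = .241, about 27.5 events. At 39 events it is .00025, or 25 expected exceedances in 100,000, which is adequate.

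**Weight of the look.** Under HR .54 the drift is |ln .54| × √(25.3/4) = 1.55, and 1 − Φ(4.64 − 1.55) = 0.10%, matching Table 2. An event falls in the CAB arm with probability .54/1.54 = .351, so the chance of 0 or 1 CAB infections among 25 is .649^25 + 25 × .351 × .649^24, about 0.03%.

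**The case against.** The misprint is hard to dispute; the case against concerns part (b).

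- **The link to the interim looks.** A reader might rely on Appendix B, where "Interim analysis procedures will follow the primary analysis definitions above". That does not carry over the test. What stands above that sentence is population, censoring, study time and endpoint, and its stated exception concerns the analysis timeframe. The link rests on section 9.1 alone, which names 7.2.2 as well as 7.3.1.
- **Purpose of the permutation rule.** It stands beside alpha = .05, where 100,000 draws are ample, and nothing says outright that its p-value is compared with a boundary alpha. That is fair. But section 9.1 cites 7.3.1 without limit, and the SAP names no other small-count method.
- **The unseen Guidelines.** They may already name the interim statistic. This stands, and the second part of the fix is conditional on it.
- **Disagreement on 1 v 24.** A reader might infer that the Z and alpha columns give opposite verdicts on that split. They do not on a like-for-like comparison. Its exact p of 1.55e-6 is below 3.48e-6, but its score Z of 4.60 falls short of 4.64. Setting an exact p against a normal-theory alpha mixes two scales, and the footnote says only approximately one event.
- **Size.** The 14% rates apply only after a nearly impossible split, and only under count/B. Under the null, 2 v 23 in either direction has probability 2 × 300/2^25 = 1.8e-5, so false crossings add about 2.6e-6 to a type I error of .05. The SAP's footnote also says that this look can be removed with virtually no effect on later boundaries.

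**Conclusion.** The point holds as a minor one, confined to the first look. The row 1 alpha is a print error by a factor of about 3.5; the row 1 Z and the later rows reproduce. On the SAP's own text, the Wald test cannot reach the first boundary and the fallback cannot resolve it, so a crossing would be either impossible or dependent on the seed, according to a convention that the SAP does not state.

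This rests on equal exposure with strata ignored for the small-count figures, on section 9.1 for applying 7.3.1 at interim looks, and on the Guidelines not saying otherwise. A reader might infer that early stopping or overall type I error control is compromised. The document does not support that. Stopping at this look has 0.1% probability under the alternative, the later boundaries stand, Wald and score differ by at most one event at the later looks, and the final analysis is unaffected.

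**What to change.** 1. In Table 2 row 1, change nominal and cumulative alpha from .000001 to .0000035.
2. Unless the Interim Monitoring Guidelines already settle it, add one sentence to 4.1.1 or 7.2.2. At any interim look with fewer than 40 events, the crossing is judged by a permutation p-value for the site-stratified log-rank (score) statistic, permuted within site. It is computed exactly or with enough draws to resolve that look's alpha, and compared with the spending-function alpha at the actual information. The Cox model stays for the hazard ratio.

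As an example, 10 million draws with (count+1)/(B+1) allow 33 exceedances at 3.48e-6. Under equal risk, 1 v 24 then expects about 15 and 2 v 23 about 194, so the seed hardly matters. An exact calculation would serve equally well.

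Cost: two table cells, one sentence and some computing time. If the first look has already passed, only the table correction and a note of the method used remain.
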